9.6 PREGNANCY

It is not known if carfilzomib is harmful to an unborn or breastfed baby. If a subject or their partner becomes pregnant while receiveing this drug, potential risks could include complications such as miscarriage or birth defects. It is not known if carfilzomib is transferred to breast milk. Potential subjects who are breastfeeding will be required to discontinue nursing during treatment with carfilzomib and for an additional 30 days following their last treatment with carfilzomib.

The FDA has assigned Irinotecan to pregnancy category D. It may cause fetal harm when administered to pregnant women. Animal studies have revealed evidence of embryotoxicity and teratogenicity. There are no controlled data in human pregnancy. If the subject or her partner becomes pregnant while receiving this drug, potential risks could include complications such as miscarriage or birth defects. Potential subjects who are breastfeeding will be required to discontinue nursing during treatment with irinotecan and for an additional 30 days following their last treatment with irinotecan.

Pregnant or breastfeeding women and women planning to become pregnant should not participate in this study. If a female subject or the female partner of a male subject is unable to become pregnant because her healthcare provider has determined that she is postmenopausal or she has had her uterus, ovaries, or both fallopian tubes removed, the use of birth control is not required during this study. If a female subject or the female partner of a male subject could become pregnant, she must let her partner know she is in the study. She must agree to discuss acceptable pregnancy prevention methods with the study physician and practice abstinence or use an acceptable method of birth control.

Patient of childbearing potential must use contraception during and for 30 days after the last dose of carfilzomib and irinotecan. Examples of contraceptive methods with a failure rate of < 1% per year include tubal ligation, male sterilization, hormonal implants, established, proper use of combined oral or injected hormonal contraceptives, and certain intrauterine devices. Alternatively, two methods (e.g., two barrier methods such as a condom and a cervical cap) may be combined to achieve a failure rate of < 1% per year. Barrier methods must always be supplemented with the use of a spermicide.

If a male subject has had a vasectomy and testing has shown that there is no sperm present in the semen, the use of birth control method in this study is not required. Otherwise, male subjects must:

- Let his female partner know he is participating in this study.
- Practice abstinence or use a condom during treatment in addition to 30 following final treatment with carfilzomib.

Male subjects must not donate sperm during treat and for an additional 30 days following their last treatment with carfilzomib. To prevent exposure of the unborn child to carfilzomib through semen, the male subject must agree to the use of a condom during vaginal sex.

If a subject or spouse or partner of a subject becomes pregnant while enrolled in this clinical trial or up to three months following administration of Carfilzomib or irinotecan, they must inform the study staff right away. The CRAB CTC Operations Office must be notified within 24 hours of the Investigator, designee, or site personnel learning of the pregnancy. Instructions are provided below.

Pregnancy Reporting by Investigator-sponsor to Amgen

Report Pregnancy and potential infant exposure including Lactation, within ten (10) calendar days of Sponsor awareness. Provide to Amgen the SAE reports associated with pregnancy. SUSARs are to be reported within twenty-four (24) hours of submitting the report to the applicable regulatory authority. (See Amgen Drug Safety and Pharmacovigilance Contact information above).

If the subject is pregnant, carfilzomib and irinotecan must be withheld.

Subjects, spouses, or partners will be followed through the outcome of the pregnancy. The Investigator will be required to report the results to the CRAB CTC Operations Office who will inform both the study sponsor as well as Amgen Drug Safety.

If the outcome of the pregnancy meets a criterion for immediate classification as an SAE spontaneous abortion (any congenital anomaly detected in an aborted fetus is to be
documented), stillbirth, neonatal death, or congenital anomaly—the Investigator should repeat the procedures for expedited reporting of SAEs as outlined above.

Any pregnancy that occurs during study participation must be reported using the Pregnancy Report Forms (please see the instructions below). To ensure subject safety, each pregnancy must be reported to the CRAB Operations Office within 24 hours of learning of its occurrence. The pregnancy must be followed-up to determine outcome, including spontaneous or voluntary termination, details of birth, and the presence or absence of any birth defects, congenital abnormalities or maternal and newborn complications and their relation to study drug. Initial and Follow-up Pregnancy Report Forms are accessible online through the study website. The CRAB CTC Operations Office will report the pregnancy and outcome to Amgen Drug Safety.

The pregnancy, breastfeeding, and birth control information in this protocol is specific to carfilzomib. There may be additional risks to an unborn child or breastfed baby from irinotecan, which is also used in this protocol. This may require study subjects to change the type and/or length of time they use birth control. The length of time breastfeeding must be avoided may also change. Subjects must be instructed to discuss this with their study physician.

Instructions for Rapid Notification of Pregnancies

Each pregnancy commencing during the study must be reported by telephone to the CRAB CTC Operations Office at [contact] within 24 hours of learning of its occurrence. Pregnancies and pregnancy follow-up should be reported as directed during the call. Any serious adverse event experienced during pregnancy must be reported as outlined in Section 9.5.1. Pregnancy follow-up must describe the outcome of the pregnancy, including any voluntary or spontaneous termination, details of the birth, the presence or absence of any congenital abnormalities, birth defects, maternal or newborn complications and their relation to the study drug.

10 CORRELATIVE STUDIES

Pharmacodynamics/Biomarkers (Phase-Ib and Phase-II): The dose dependent proteasome inhibition on LMP7 and b5 proteasome subunits will be determined in purified PBMC to ensure that the intended effect is achieved in this surrogate tissue. Correlative PD biomarkers will be collected from all Phase 1b subjects (up to 24) and the first 15 subjects from each stratum of the Phase 2 portion. If a patient is registered as one of the first 15 patients in each stratum, the site will receive notice of for pharmacokinetic sampling via an auto-email. The response to irinotecan depends on the expression of topoisomerase-I (topo-I). Here, we will determine the expression of topo-I in banked tissues to determine if response correlates with Topo-I expression. Furthermore, to determine the effect of irinotecan and carfilzomib, we will measure the time dependent expression of gamma-H2AX and Topoisomerase-I in purified PBMC. We expect that irinotecan/SN-38 mediated DNA damage will increase the expression of gamma-H2AX. As topoisomerase-I undergoes proteasome mediated degradation, the expression of gamma H2AX declines. We expect that the combination with carfilzomib will increase Topo-I stability and sustained gamma-H2AX expression.

10.1 LABORATORY CORRELATIVE STUDIES

Pharmacodynamics (Phase-Ib and Phase-II):

- Carfilzomib proteasome chymotrypsin-like activity in PBMC (LMP7 and b5 activity) in all subjects in phase Ib and in 15 subjects in each cohort from phase II study.
- Expression of gamma-H2AX and Topoisomerase-I in PBMC in all subjects in all subjects in phase Ib and in 15 subjects in each cohort from phase II study.
- Expression of Topoisomerase-I in banked tissues in all subjects. Ten unstained slides on charged glass slides are preferable.

Carfilzomib mediated proteasome inhibition will be measured in purified PBMC using commercially available reagents. Irinotecan mediated DNA damage and the effect of carfilzomib in this process will be determined by time dependent changes in gamma-H2AX and Topoisomerase-I expression in purified PBMC. Blood samples for isolation of monocytes will be collected in BD Vacutainer CPT Mononuclear Cell Preparation Tubes (8mL) on Day 1

and 2 of Cycle 1. When available, tumor tissues will be obtained from participating sites to assess the expression of Topoisomerase-I using immunohistochemistry in all subjects.

Collection of Specimen(s)

Day 01: Sampling times are relative to the start of irinotecan infusion time: Pre-irinotecan, 90 min., 2 hr, and 5.5 hr.

Day 02: Pre-carfilzomib infusion.

Handling of Specimens(s)

- Process each sample (both CPT tubes) individually within 5 minutes following sample collection. Samples should not be placed on ice.
- 2. Gently invert the tube 8 to 10 times to mix the anticoagulant with the whole blood. Do not shake the tube.
- 3. Keep sample tube at room temperature in the upright position at all times before and after blood collection and while waiting for centrifugation.
- Centrifuge the CPT® tubes containing blood sample at room temperature (18-25°C) in a horizontal rotor (swing-out head) for 20 minutes at 1800xG.
- 5. Gently inverted 5-10 times to re-suspend cells (whitish layer)
- 6. Using a disposable transfer pipet transfer the plasma/PBMC suspension from the two CPT® 4mL tubes into a single, 15 mL centrifuge tube
- Centrifuge the 15 mL tube at 1800xG, for 2 minutes at room temperature (18-25°C). Carefully pipette and discard all the plasma supernatant.
- 8. Allow samples to stand upright for 2 minutes on ice and carefully aspirate and discard any additional supernatant. NOTE: Please use care so that the cell pellet is not disturbed
- 9. Store tubes on dry ice or transfer to -80°C for storage until shipping. Record the time the sample was placed on dry ice or into -80°C as the "time processed" on the eCRF.
- 10. Send a hard copy of the eCRF "Specimen Collection Form" with this package

Samples should be shipped on Monday, Tuesday or Wednesday only. Please send notification of shipping via email to [name] on the day of shipment.

Shipping of Specimen(s)
Samples should be shipped on dry ice to: [name]
Department of Pharmaceutical Sciences
College of Pharmacy
University of Kentucky
[name]
E-mail: [contact]
[contact] Office
[contact] Fax

11 STATISTICAL ANALYSIS

The accrual rate for the phase I component is anticipated to be approximately 2-3 subjects per month, with a completion time of 6-9 months. The accrual rate for the phase II component is anticipated to be 3-5 subjects per month and will proceed separately in two strata (platinum-sensitive vs. platinum-refractory subjects).

The primary endpoint for the phase II trial is the percent of subjects alive at six months. We will consider the combination of Carfilzomib and Irinotecan to be of interest in platinum sensitive subjects if the proportion of subjects alive at six months is 60% or greater, compared to a benchmark six-month survival rate of 40%. With a total of 40 eligible subjects treated at the RP2D in the platinum sensitive stratum, we will be able to test the null hypothesis that the true survival rate at six months is at most 40% versus the alternative that the true survival rate at six months is 60% or greater with a power of 79% and a one sided significance level, alpha of .04. According to this design, if at least 22 subjects out of 40 are alive at six months, we can reject the null hypothesis of a 40% six-month survival rate. This will be considered adequate evidence of promising activity for this regimen, and it may be recommended for further testing in subsequent studies. If fewer than 22 subjects are alive at 6 months, we will consider the regimen insufficiently active in this subject population. We will consider the combination of Carfilzonib and Irinotecan to be of interest in *platinum refractory* subjects if the proportion of subjects alive at six months is 45% or greater, compared to a benchmark sixmonth survival rate of 25%. For the platinum refractory stratum, 40 evaluable subjects will enable us to test the null hypothesis that the true survival rate at six months is at most 25% versus the alternative that the true survival rate at six months is 45% or greater with a power of 86% and a one-sided significance level of .054. If at least 15 subjects out of 40 are alive at six months, this will be considered adequate evidence of promising activity, and the regimen may be recommended for further testing in subsequent studies. If fewer than 15 subjects are alive at 6 months, we will consider the regimen insufficiently active in this subject population.

Secondary endpoints for both phases include response rates, safety/tolerability and the rates of specific adverse events, progression-free survival and biomarker endpoints as described in sections 10.1 and 10.2. With 40 eligible subjects in each stratum, the 6 month survival rate,

and the rates of individual adverse events, can be calculated to within at most +/-16% (95% confidence interval) for each individual stratum. Due to the limited sample size in a Phase II setting, correlative studies will be considered exploratory in nature and will be used to formulate hypotheses that can be tested using correlative data from a Phase III setting.

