Camptothecins inhibit topoisomerase I. As a class, camptothecins have shown efficacy in small cell lung cancer in a variety of settings. Several phase II studies demonstrated clinical benefit including the trials of Perez-Soler et al., who showed clinical benefit in 10 out of 32 subjects with extensive stage SCLC in the second line with parenteral topotecan, 1.25 mg/m² daily on Days 1-5 every 21 days^[2] and Ardizzoni et al. who used a higher dose (1.5 mg/m²) but the same schedule, in

101 subjects with relapsed extensive stage disease with median overall survival (6.9 months for sensitive subjects and 4.7 months for refractory subjects (P=0.002).^[25] The pivotal phase III study which led to FDA approval of topotecan in relapsed small cell lung cancer was by Von Pawel et al,^[26] and included 211 subjects with sensitive (> 60 days since prior therapy) relapse and randomized them to either topotecan (107 subjects) daily for 5 days or to cyclophosphamide, doxorubicin, and vincristine (CAV), each given every 21 days. Topotecan showed no significant improvement in the median time to progression (13.3 weeks vs.12.3 weeks, p=0.552) or median survival (25 weeks vs. 24.7 weeks, p=0.795), however, subjects treated with topotecan had improvement in cancer-related symptoms (dyspnea, hoarseness, anorexia, and fatigue) as well as hematologic toxicity.

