Another camptothecin, irinotecan, has established activity in small cell lung cancer, as well as nonsmall cell lung cancer, colorectal cancer and ovarian cancer. As a single agent, Negoro and colleagues treated 35 subjects with 100 mg/m² with a response rate of 50% in untreated subjects and 33% in previously treated subjects.^[27] Additional phase II studies of weekly irinotecan by Masuda. et al^[28], demonstrated an objective response rate of 47% and a median survival of 26 weeks (similar to other camptothecins). Le Chevalier and colleagues^[29] used an every 3-week schedule of irinotecan, 350 mg/m², given to 32 chemotherapy-naive SCLC subjects and showed an objective response rate of 16% and a median survival of 4.5 months. Thus, the median survival of camptothecins in the second –line setting in SCLC ranges from 24 to 35 weeks, with those subjects in sensitive relapse having a median survival of 4 to 8 weeks longer than those with refractory relapse. In addition, irinotecan has also been demonstrated to be effective when combined with cisplatin in the front line setting, in extensive stage small cell lung cancer. A Japanese study by Noda, and colleagues demonstrated superiority of this combination when compared to cisplatin and etoposide.^[30] While, these results were not replicated in a Southwest Oncology Group (SWOG) study, the combination is considered an alternative to cisplatin and etoposide in this disease.^[31] The similar efficacy and favorable toxicity of weekly irinotecan delivery justifies its use in the current proposal.

Rationale for Carfilzomib sequencing and combination with topoisomerase inhibitors

Sequencing information for Carfilzomib and other chemotherapeutic drugs is limited. Extrapolating from data using bortezomib, it was shown by several groups that bortezomib sensitized NSCLC and pancreatic cancer cells to gemcitabine, as well as inducing apoptosis in vitro and in vivo.^{[18],[32]}

Sequence dependent enhanced activity was observed by Mortenson and colleagues when bortezomib was given after gemcitabine/carboplatin in NSCLC cell line studies.^[23]

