3.1 STUDY DESIGN

1. Phase 1b: standard 3+3 design using five dose levels of Carfilzomib. Two dose de-escalations are built into the protocol for safety.

3+3 design	Doses	
	Carfilzomib*	Irinotecan
Cohort -2	$20 mg/m^2$	$75 mg/m^2$
Cohort -1	20 mg/m^2	100 mg/m^2
Cohort 1	$20/27 mg/m^2$	$125 mg/m^2$
Cohort 2	$20/36 mg/m^2$	$125 mg/m^2$
Cohort 3	$20/45 mg/m^2$	$125 mg/m^2$
Cohort 4	$20/56 mg/m^2$	$125 mg/m^2$
Cohort 5	20/70 mg/m ²	$125 mg/m^2$

Table 2. Dose escalation schema

Cycle 1 Day 1 & Day 2 doses are 20 mg/m2. All subsequent days as specified, i.e. 20/27 mg/m2 means Cycle 1 Day 1 & Day 2 doses are 20 mg/m2 and all other days are 27mg/m2.

Phase II: Stratified, single arm trial using MTD of Carfilzomib 20/36 mg/m2 with Irinotecan 125 mg/m2 as established from Phase Ib, in up to 88 small cell lung cancer subjects who have relapsed on a prior platinum regimen.

Stratification for phase II component:. Patients will be accrued in two separate strata; each stratum has its own accrual target and may be closed or open to accrual independently:

- a. Platinum sensitive disease: initial response to platinum-based chemotherapy with progression > 90 days after last treatment.
- b. Platinum refractory disease: No response to platinum-based chemotherapy or progression within 90 days of completing platinum-based therapy. Subjects that progressed during or within one month of completion of platinum-based chemotherapy will be excluded.

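### Do the 40% and 25% six-month benchmarks need changing, given that Section 11 names no source and some background medians look higher?

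*Combined protocol and SAP*

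**What the plan says.** Section 11 makes the proportion alive at six months the Phase II primary endpoint, judged separately in two strata of 40.

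- **Platinum sensitive:** the regimen is of interest if that proportion "is 60% or greater, compared to a benchmark six-month survival rate of 40" percent. The rule is at least 22 of 40 alive, with stated power 79% and one-sided alpha .04.
- **Platinum refractory:** the target "is 45% or greater, compared to a benchmark sixmonth survival rate of 25" percent. The rule is at least 15 of 40 alive, with stated power 86% and alpha .054.

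Of a pass in the sensitive stratum, Section 11 says: "This will be considered adequate evidence of promising activity for this regimen". The regimen may then be recommended for further study. The refractory wording is similar.

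Neither benchmark carries a citation or derivation, and no other section gives a historical six-month rate. The nearest material is the Camptothecins part of Section 1.5:

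- a phase II topotecan study with medians of "6.9 months for sensitive subjects and 4.7 months for refractory subjects";
- a phase III study of topotecan against a three-drug regimen in "211 subjects with sensitive (> 60 days since prior therapy) relapse", with "median survival (25 weeks vs. 24.7 weeks, p=0.795";
- a three-weekly irinotecan study with a median of 4.5 months;
- a summary that the camptothecin median in the second-line "setting in SCLC ranges from 24 to 35 weeks", with sensitive relapse 4 to 8 weeks better than refractory.

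**The concern.** In a single-arm trial the null rate stands in for the control group, so alpha means only as much as the benchmark does. A reader who turns from Section 11 to Section 1.5 finds two studies with medians for sensitive relapse, and both seem to sit above 40%. A 6.9-month median means at least half of that sample was alive at six months, whatever the shape of the curve. A 25-week median falls about a week short of six months, and survival would have to drop from 50% to 40% in that week to agree with the benchmark.

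Entry to this trial's sensitive stratum ("initial response to platinum-based chemotherapy with progression > 90 days after last treatment") is also stricter than the 60-day rule of the phase III study, so the definition alone does not explain a lower figure.

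If 40% were too low, a combination no better than a camptothecin alone could be called promising far more often than 4% of the time, and a later trial might be launched on that basis.

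**Working it through.** **1. The plan's own figures.** Exact binomial, n = 40:

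| Stratum | Rule | Alpha at the null | Power at the alternative |
|---|---|---|---|
| Sensitive | at least 22 | .039 at 40% (stated .04) | .791 at 60% (stated 79%) |
| Refractory | at least 15 | .054 at 25% (stated .054) | .867 at 45% (stated 86%) |

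The design arithmetic holds.

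**2. From medians to six-month survival.** Six months is 26.09 weeks. With Weibull shape k (k = 1 is exponential), S(6) = 0.5^((26.09/median in weeks)^k).

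| Median (Section 1.5) | S(6), exponential | Chance of at least 22 of 40 |
|---|---|---|
| 6.9 months, sensitive | 0.5^(6/6.9) = .547 | .55 |
| 25 weeks, sensitive | 0.5^(26.09/25) = .485 | .254 |
| 24 weeks, low end of summary | 0.5^(26.09/24) = .471 | .199 |
| 4.5 months, irinotecan | 0.5^(6/4.5) = .397 | .036 |

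At exactly 50%, the least that a 6.9-month median allows, the chance is .318. For the 25-week median it runs from .171 (k = 2.5) to .266 (k = 0.8).

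**3. Could a 25-week median still give 40%?** The gap is 26.09 − 25 = 1.09 weeks, or 7.6 days. Falling from .50 to .40 needs a hazard of −ln(.8)/1.09 = .205 per week. The average over the first 25 weeks is ln 2/25 = .0277, so the ratio is 7.4. Taken at face value, curve shape does not close the gap.

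**4. Sampling error.** The phase III topotecan arm had 107 subjects. Assuming complete six-month follow-up and an exponential curve, .485 ± 1.96 × √(.485 × .515/107) = .485 ± .095, or about 39% to 58%. That includes 40%. The 6.9-month figure comes from an unstated part of 101 subjects.

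**5. The irinotecan study.** Section 1.5 calls its 32 subjects chemotherapy-naive. The title of reference 29 in Section 15 says they had progressed after responding to first-line chemotherapy. If the title is right, this is a relapse-after-response median for this trial's own backbone drug, and its 39.7% sits on the benchmark. The figure depends on shape: 41.8% at k = 0.8 and 29.2% at k = 2.

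**6. Refractory stratum.** Taking 4 and 8 weeks off 4.5 months (19.57 weeks) gives medians of 15.57 and 11.57 weeks, and S(6) = .313 and .209, which bracket 25%. The 4.7-month topotecan median gives .413 if exponential and .279 at k = 2.5. The documents do not settle this one.

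**7. The summary range.** The refractory median of 4.7 months is 4.7 × 26.09/6 = 20.4 weeks, below the 24-week floor. The longest second-line median cited, 6.9 months, is 30.0 weeks, short of the 35-week ceiling. The range covers second-line use generally, so it is a loose guide to sensitive relapse.

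**8. Cost of moving the sensitive null, keeping n = 40 and alpha at most .05:**

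| Null | Cut-off | Alpha | Power at 60% |
|---|---|---|---|
| 48.5% | 26 | .026 | .317 |
| 50% | 26 | .040 | .317 |
| 54.7% | 28 | .036 | .129 |

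To regain about 79% power at 60% against 48.5%, the stratum would need 118 subjects (cut-off 67). The alternative is to keep 40 subjects and raise the target: against a 50% null, the 26-of-40 rule has power .807 at 70%.

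**The case for a change.** The strongest case for acting is that the omission is real and cheap to repair. The nulls carry the whole Phase II decision. The two medians the protocol ties explicitly to sensitive relapse both point above 40%. The one figure that supports 40% is described inconsistently between the text and its reference. Two or three sentences in Section 11 would settle what 40% stands for. The 26-week irinotecan median has a similar mismatch, since reference 28 is titled as a phase I topotecan study in non-small-cell lung cancer.

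Much of this stands. There is no stated source, the 6.9-month and 25-week figures do imply more than 40% at face value, and the two references need tidying.

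Two things do not stand. First, it is too strong to say that the background as a whole points higher, given the irinotecan median, the sampling error in step 4 and the entry criteria. Section 4.1 admits performance status 2 in Phase II, which could lower survival, while the 90-day rule could raise it; the documents do not report performance status for the cited studies. Second, the .199 to .318 chances are not error rates of the stated test. If true survival is 48.5%, rejecting a null of at most 40% is correct. They become false passes only if camptothecin-level survival is put in place of the stated null. Section 11 does not claim to test that, nor to isolate carfilzomib's contribution.

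**Conclusion.** No change to the plan follows. The gap is one of documentation: the source of 40% and 25% is not written down, and two citations in Section 1.5 do not match their reference titles. Neither touches a null, a cut-off, the sample size, the interim rule or any number the analysis will produce.

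The documents do not show that 40% is wrong. They support values from about 40% (irinotecan, if reference 29's title is right) to about 55% (the phase II topotecan study), under an exponential assumption and with sampling error wide enough to include 40% for the phase III arm. For 25% they show no clear conflict.

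Choosing a higher sensitive null would be a trade-off and not a correction. It would bring power at 60% down from 79% to about 32%, or require 118 subjects in that stratum, or move the target to about 70%. A modest benchmark is a defensible choice for a screening trial whose only consequence is a possible recommendation for further testing.

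Readers who prefer another benchmark lose little. Section 11.3 plans Kaplan-Meier survival by stratum, and Section 11 gives a 95% precision of at most ±16 points, so the observed rate can be set against 50% directly. At 40 subjects, 26 alive is the count that would exceed a 50% null at one-sided .05. Whoever writes the report can name the source of the benchmarks there.
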